IPC	Infection Prevention and Control
JMP	Joint Monitoring Programme
KII	Key Informant Interview
LMIC	Low and Middle-Income Country
LoRaWAN	Low-Power, Wide Area Networking Protocol
NGO	Non-Governmental Organization
Kofam	Koordinationsstelle Forschung am Menschen (Federal Office of Public Health's (FOPH) portal for human research in Switzerland)
ODK	Open Data Kit
PHCF	Primary Health Care Facility
RANAS	Risk, Attitude, Norm, Ability and Self-regulation
SDC	Swiss Agency for Development and Cooperation

SDG	Sustainable Development Goal
Swiss TPH	Swiss Tropical and Public Health Institute
Tdh	Terre Des Hommes
ToA	Theory Of Action
ToC	Theory Of Change
UNICEF	United Nations Children's Fund
WASH	Water, Sanitation and Hygiene
WASH FIT	Water and Sanitation for Health Facility Improvement Tool
WHO	World Health Organization

IV. Synopsis

Project Leader	PD [name]
Study Title	hands4health: Hand hygiene, water quality and sanitation in primary health care not connected to functional water supply system: a cluster-randomized controlled trial in Mali and Burkina Faso
Short Title/Study ID	Hand hygiene intervention in primary health care
Protocol Version and Date	Version 1, 17.01.2023
Study Category with Rationale	Non-clinical study, risk category A: no drugs are being tested, and only hand-rinse samples are being taken
Background and Rationale	On the African continent, more than half of the population does not have access to a handwashing facility with water and soap at home. This inaccessibility contributes to the spread of communicable diseases, such as diarrhea. Countries affected by humanitarian emergencies are particularly vulnerable to water shortages and a lack of hygiene. This lack is particularly problematic in health care settings to avoid health care associated infections. Data about hand hygiene or the success of hygiene interventions in primary health care facilities (PHCFs) in conflict settings is scarce. Therefore, the “hands4health” project will collect data about hand hygiene in PHCFs and then administer a hand hygiene intervention package containing handwashing stations and behaviour change in PHCFs bordering conflict regions in Mali and Burkina Faso.
Objective(s)	
Primary objective: Evaluate the effects of the comprehensive h4h handwashing intervention on hand hygiene in PHCFs in Mali and Burkina Faso.
 
Secondary objectives:
 
 1) Assess hygiene-related risks, attitudes, norms, abilities and self-regulation (RANAS) behavioural factors of health care providers 2) Assess the impact of the h4h intervention package on hygiene-related RANAS behavioural factors of health care providers 3) Explore perceived effects on health and wellbeing of the hands4health intervention package in PHCFs
Primary Endpoint Secondary Endpoints	
The primary endpoint of this study will be good handwashing practice defined as health care workers (HCWs) who wash their hands with water and soap almost always in the five critical moments of the World Health Organization assessed by structured handwashing observations. Critical moments are:
 
 i) Before touching a patient ii) Before clean/aseptic procedures iii) After risk/exposure to body fluids iv) After touching a patient v) After touching a patient’s surroundings 
The secondary endpoints in the survey are:
 
 A) Self reported handwashing practice answered for each critical moment on a Likert scale ranging from almost never to almost always.

	
B) Number of total coliforms and E.coli colony-forming units (CFUs) per hand before handwashing.
 
C) Hygiene-related health outcomes which are summarized in table 3. The health outcomes will be reassessed with local experts of the respective countries to assure feasibility before the start of the intervention.

Study Design
	
Overall project: Multi-center cluster-randomized controlled trial (cRCT) design.
 
Module 1-3 will be repeated three times within the cRCT at baseline, two months post-intervention and at endline. Module 4 data collection will take place in both study arms longitudinally starting after the intervention has been implemented. Module 5 and 6 are qualitative focus group discussions (FGDs) and interviews and will take place after the second round of data collection in Modules 1-3. For Module 2, only a maximum of 10 HCWs per facility will be observed.


Inclusion/Exclusion Criteria
	
Study participants will be HCWs of the PHCFs which were chosen to be included in this study.
 
Inclusion criteria Modules 1-3: PHCFs were chosen based on accessibility for the study teams, not having a water source directly connected to the building of the facility, having a maternity ward, having at least five employees and being impacted by conflict. All of the HCWs who are present in the PHCFs of the day of data collection will be invited to participate in the project for Modules 1 and 3.
 
HCWs must fulfil all the inclusion criteria:
 
 - Minimum age of 18 years - HCWs, men and women, who are in direct (body) contact with the patients 
Exclusion criteria Modules 1-3: HCW participants must not fulfil any of the following exclusion criteria:
 
 - HCWs, whose primary occupation is not in the PHCF of the h4h project - Suffering from any skin conditions not allowing the HCW to use soap or alcoholic hand rub - Refusals to participate 
Inclusion/Exclusion criteria Module 4: As the data will be collected on the health care facility level, all facilities in the project will be included.
 
Inclusion criteria Module 5:
 
 - HCWs of the intervention facilities - Minimum age of 18 years 
Exclusion criteria Module 5: Refusals to participate.
 
Inclusion criteria Module 6:
 
 - The participant needs to be: 
 a) a stakeholder within the community, state, region or country of the intervention who's position is related in any way to WASH in HCFs b) working in one of the intervention PHCFs. They do not need to be HCWs, they can also be hygiene technicians or in a leading position of the facilities.

	
- Minimum age of 18 years
 
Exclusion criteria Module 6: Refusals to participate

Measurements and Procedures	
Different methods across modules will be used to achieve the objectives of this project. These modules will include qualitative and quantitative data approaches in order to enable a triangulation of the overall project results. The following modules will be used in the cRCT and the overall project: (i) Module 1: Combined RANAS and knowledge, attitudes and practice (KAP) survey, (ii) Module 2: Structured handwashing observations, (iii) Module 3: Microbiological analysis of hand rinse samples, (iv) Module 4: Diary approach for pre-defined health outcomes, (v) Module 5:FGDs and (vi) Module 6: Key informant interviews (KIIs). Endpoints of Modules 1-3 will be assessed at baseline, at follow-up and endline of the cRCT. Module 4 will be used to collect data longitudinally over the course of 9 months. Module 5 and 6 will be used in the middle of the intervention phase in the intervention groups.

Number of Participants with Rationale (if no Power Analysis conducted)	
The sample size calculation yielded a minimum of 20 health care facilities per country. With political instability and other factors which might lead to a loss of follow-up, we increased the sample size to 24 health care facilities per country. This will lead to 48 health care facilities in total. We estimate a median of 6 HCWs working in the facilities and a mean number of 5 observed handwashings per person. This would lead to about 384 participants in the entire study.
 
For Modules 1 and 3, all HCWs who are present during data collection and eligible will be asked to participate in the study. For Module 2, the observations a maximum of 10 HCWs per PHCF will be followed in order to avoid disturbing the daily routines of the PHCF too much. Module 4 follows the sample size calculation of the cRCT design, hence 24 PHCFs will be monitored. For Module 5, 6-10 FGDs will be administered and for Module 6, 10-20 interviews.

Study Duration	14 months
Study Schedule	January 2023 of First-Participant-In (planned) March 2024 of Last-Participant-Out (planned)
Investigator(s)	
[name]. [name] and [name] Swiss Tropical and Public Health Institute [name] [contact] [contact] and [contact]
 
[name] Terre des hommes Mali [name] Phone: [name] [contact]
 
[name] Terre des hommes Burkina Faso [name] Phone : [contact]
 
[name] Skat Foundation [name]

	
[name] Phone [contact]

Study Centre(s)	Multinational: Mali, Burkina Faso
Statistical Analysis incl. Power Analysis	
To determine the required sample size, we run a series of simulations using the software R. Assuming a mean number of six staff members (range two to nine) per health facility and a mean number of five times a person was supposed to wash their hands (SD=5) and an intra cluster correlation coefficient of 0.15, we need to enrol 10 health facilities in each trial arm to detect difference of 15%-points (30% control versus 45% intervention) with 81% power at a two-sided 5% significance level. To account for potential loss to follow-up we aim to enrol in total 24 health facilities.
 
Baseline characteristics will be summarized using descriptive statistics. The difference between two study arms at follow-up will be investigated using mixed effect logistic regression models with random intercepts for health care facilities using the available case population analysed according to the intention-to-treat principles. In the primary analysis only the intervention will be included as predictor.

Ethical consideration	
This project will be carried out in accordance with the research plan outlined in this protocol and with principles enunciated in the current version of the Declaration of Helsinki / Essentials of Good Epidemiological Practice issued by Public Health Switzerland (EGEP) / ISO EN 14155 / CIOMS International Ethical Guidelines for epidemiological studies 2009 as well as all national legal requirements and guidelines as applicable. This protocol will be reviewed by the Ethikkommission Nordwest- und Zentralschweiz (EKNZ, Ethics Committee of Northern and Central Switzerland) and also be reviewed and approved by the National Institute of Public Health (INSP) in Mali, and the Comité d'Ethique pour la Recherche en Santé (CERS) in Burkina Faso. This trial will be registered at the U.S. National Library of Medicine under https://www.clinicaltrials.gov.

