4.4 Study duration and duration of participant's participation

HCWs will be regularly approached for data collection. First, the data collection phase starts with the observations and is then followed by the Ranas questionnaire and the hand-rinse samples (Figure 3). For practical reasons, the hand-rinse samples can be taken right after the questionnaire.

[figure not shown]

Figure 4: Flow-chart of data collection activities at baseline, follow-up and endline of the project depicting observations, the Ranas questionnaire and the hand-rinse samples.

The observations will take approximately 30 minutes to one hour per HCW depending on how many patients visit and hence how many handwashing opportunities arise. The questionnaire will take a maximum of 40 minutes and the hand-rinse samples about 10 minutes. This means that for the Ranas questionnaire and the hand-rinse samples together with the informed consent, the participant will be asked for about an hour of his/her time.

Entering the pre-defined health outcomes in the diary over the course of the year will not take much time of the HCWs. To write down an event will take the HCW about two minutes per event.

Finally, the HCWs of the 12 intervention facilities will be asked to take part in FGDs or interviews. This should not take them longer than one hour. KIIs with stakeholders outside of the health care facilities will also be limited to one hour.

H4H
Version 1 17.01.2023

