5.2 Inclusion criteria

Study participants will be HCWs of the PHCFs which were chosen to be included in this study. PHCFs were chosen based on accessibility for the study teams, not having a water source directly connected to the building of the facility, having a maternity ward, having at least five employees and being impacted by conflict. All of the HCWs who are present in the PHCFs of the day of data collection will be invited to participate in the project for Modules 1 and 3.

Inclusion criteria Modules 1-3: HCWs must fulfil all the inclusion criteria:

- Minimum age of 18 years
- HCWs, men and women, who are in direct (body) contact with the patients

During the handwashing observations, health workers will consult with patients. In order to protect patients, they must meet these inclusion criteria for an observer to be allowed into the consultation room with them:

- Minimum age of 18 years or be accompanied by a legal guardian 18 years or older.
- Going to the SSE for a physical examination, injections/vaccinations or blood test.
- Oral consent to enter the room with them

Inclusion criteria Module 4: As the data will be collected on the health care facility level, all facilities in the project will be included.

Inclusion criteria Module 5:

- HCWs of the intervention facilities
- Minimum age of 18 years

Inclusion criteria Module 6:

- The participant needs to be:
 - a) a stakeholder within the community, state, region or country of the intervention who's position is related in any way to WASH in HCFs
 - b) working in one of the intervention PHCFs. They do not need to be HCWs, they can also be hygiene technicians or in a leading position of the facilities.
- Minimum age of 18 years

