6.2 Determination of sample size

To determine the required sample size, we run a series of simulation using the software R. Assuming a mean number of six staff members (range two to nine) per health facility and a mean number of five times a person was supposed to wash their hands ($SD=5$) and an intra cluster correlation coefficient of 0.15, we need to enrol 10 health facilities in each trial arm to detect difference of 15%-points in the proportion of handwashing during the five critical moments of the WHO (30% control versus 45% intervention) with 81% power at a two-sided 5% significance level. To account for potential loss to follow-up we aim to enrol in total 24 health facilities.

For Modules 1 and 3, all HCWs who are present during data collection and eligible will be asked to participate in the study. For Module 2, the observations a maximum of 10 HCWs per PHCF will be followed in order to avoid disturbing the daily routines of the PHCF too much. Module 4 follows the sample size calculation of the cRCT design, hence 24 PHCFs will be monitored. For Module 5, 6-10 FGDs will be administered and for Module 6, 10-20 interviews.

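### The stated 384 participants do not follow from 48 facilities with 6 health care workers each (288), and the number of facilities to enrol is 48 in one place and 24 in others

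*Combined protocol and SAP*

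**What the plan says.** The Synopsis row on the number of participants starts from the power calculation: "The sample size calculation yielded a minimum of 20 health care facilities per country". It then allows for instability and other losses: "we increased the sample size to 24 health care facilities per country". It draws the total: "This will lead to 48 health care facilities in total". Taking a median of 6 health care workers (HCWs) per facility, it concludes: "This would lead to about 384 participants in the entire study".

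The power text appears in the Synopsis row on statistical analysis and again in section 6.2. It assumes a mean of six staff per facility (range two to nine), arrives at 10 facilities per arm, and then states: "To account for potential loss to follow-up we aim to enrol in total 24 health facilities". Section 4 describes the choice of 24 facilities and their randomisation to two arms. Section 4.4 says that "the HCWs of the 12 intervention facilities will be asked to take part" in focus groups or interviews.

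For Module 4 (the health-outcome diary), the Synopsis participant row and section 6.2 say "hence 24 PHCFs will be monitored". The eligibility text in the Synopsis and in section 5.2 says "all facilities in the project will be included".

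**The concern.** Two figures that a reader takes from the sample-size text cannot be relied on. The participant total is not the product of the inputs beside it. The number of clusters to be enrolled, a core design quantity in a cluster-randomised trial, takes two values that differ by a factor of two.

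The second matters more. The Synopsis presents 20 facilities as a minimum for each country. Section 6.2 presents the same 20 (10 per arm) followed by 24 in total, and section 6.1.1 states one hypothesis covering both countries. A reader cannot tell whether the 81% power applies within each country or to the two countries pooled, nor how many facilities will supply Module 4 data.

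**Working it through.** **Step 1: try to reproduce 384.** The inputs, from the Synopsis participant row, are 24 facilities per country, 2 countries and 6 HCWs per facility.

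- Facilities: 24 x 2 = 48, as stated.
- Participants: 48 x 6 = 288, not 384.
- Difference: 384 - 288 = 96; 384 / 288 = 1.33, an excess of 33%.

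The Synopsis figure of 6 is a median, and a median times a count is not strictly a total. That does not help here, because the mean in section 6.2 is also six.

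**Step 2: what would give 384?**

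- With 48 facilities: 384 / 48 = 8 HCWs each.
- With 24 facilities: 384 / 24 = 16 each.
- With 6 HCWs each: 384 / 6 = 64 facilities.

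None of these is a planning assumption. The value 8.0 occurs only in Table 1, as the median number of employed staff in the first Burkina Faso pilot (BF1). Because of security concerns there, a second pilot was run in more accessible facilities. Since 48 x 8 = 384 exactly, BF1 may be where the figure came from, but the protocol does not say so.

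**Step 3: other routes.**

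- Pilot medians for Mali and BF1: 24 x 6 + 24 x 8 = 336.
- Pilot medians for Mali and the second Burkina Faso pilot (5.0): 24 x 6 + 24 x 5 = 264.
- Allowance for loss: 1 - 288/384 = 25% would be needed. No such rate is stated, and loss is already covered by going from 20 to 24 facilities per country.
- Adding the Module 6 interviews (10 to 20): at most 288 + 20 = 308, or 288 + 40 = 328 if that number is per country.

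None of these reaches 384.

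**Step 4: the facility counts side by side.**

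| Place | Facilities |
|---|---|
| Synopsis, number of participants | 24 per country, 48 in total |
| Synopsis, statistical analysis; section 6.2 | 24 in total |
| Section 4 | 24 randomised to two arms (Figure 3 caption refers to Mali) |
| Section 4.4 | 12 intervention facilities |
| Module 4, Synopsis participant row; section 6.2 | 24 |
| Module 4, Synopsis eligibility; section 5.2 | all in the project |

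With equal arms, 48 in total gives 48 / 2 = 24 intervention facilities, and 24 in total gives 24 / 2 = 12. The 12 in section 4.4 therefore fits 24 in total, or one country's share of 48. The Synopsis participant row itself holds both 48 for the trial and 24 for Module 4.

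**Step 5: what each reading implies.**

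- *48 in total:* 24 per country exceeds the minimum of 20 per country; about 288 participants.
- *24 in total:* 24 exceeds the 2 x 10 = 20 that section 6.2 requires for a single pooled comparison; about 24 x 6 = 144 participants. An even split (an assumption) would give 12 per country, below the Synopsis minimum of 20 per country, so that minimum could not stand.

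**The case against.** The strongest reply is that the facility conflict is only an omission of *per country*. The calculation gives 10 per arm, hence 20. The Synopsis calls that same 20 a per-country number, raises it to 24 per country and doubles it to 48. The Figure 3 caption in section 4 is limited to Mali. On that reading the 24 in section 4, the 12 in section 4.4 and the 24 for Module 4 are all per-country figures. The focus groups show the same pattern: section 5.1 gives 6 to 10 per country, while section 6.2 gives 6 to 10 without qualification. This explanation is probably right. It does not remove the conflict, because the power text, stated twice, says 24 *in total* in a two-country trial.

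For the 384, one can say that a mean of 8 may coexist with a median of 6, or that staff who join between the three survey rounds add participants. The first fails on the stated mean of six. The second is possible, but the protocol does not offer it as the derivation.

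A reader might also be tempted to go further, and there the documents give no support:

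- *That 288 is a ceiling because six is generous.* Table 1 describes potential facilities, whereas enrolment requires at least five employees. The planning range of two to nine starts below that floor, so the six may already be the HCWs available for observation. New staff over three rounds and outside stakeholders in Module 6 could also add people.
- *That the trial will have only 12 facilities per country, or diary data from only half its facilities.* The first arises only if 24 in total is meant and evenly split, the second only if 48 are enrolled and Module 4 is truly limited to 24. Neither arises on the per-country reading.

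**Conclusion.** The point holds on both counts. The figure of 384 is not reproducible from the protocol's inputs: they give about 288, so it is overstated by 96 (33%), or about 144 participants if there are 24 facilities in all. The number of facilities to be enrolled is stated as both 48 and 24 in total, and Module 4 as both 24 facilities and all of them.

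The consequence is limited. The participant total does not enter the power simulation, so it would be wrong to infer that correcting it changes the stated 81%. The facility count is the more serious part, because it decides whether the power statement is read per country or pooled. Even if 24 in total were meant, the pooled comparison would still exceed the 20 facilities that section 6.2 asks for. What would fall is the claim of a minimum of 20 per country.

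The 288 and 144 rest on six HCWs per facility as a mean, as section 6.2 states, and count each HCW once.

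**What to change.** Use one facility count throughout, and say in section 6.2 whether the power statement applies to each country or to both pooled.

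- *If 48 is meant:* write 24 per country and 48 in total in the Synopsis statistical row, section 4 and section 6.2. Write 12 intervention facilities per country in section 4.4. State that Module 4 runs in all 48, in agreement with section 5.2. Replace 384 by about 288, or give the inputs that lead to 384.
- *If 24 in total is meant:* withdraw the minimum of 20 per country, the 24 per country and the 48 from the Synopsis, and give about 144 participants. The Module 4 figures then agree as they stand.

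The cost is protocol wording and a smaller stated participant number. No added enrolment is needed.

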2 BACKGROUND INFORMATION

2.1 The effects of hand hygiene on health

Globally, about 3.3% of deaths are attributable to effects of insufficient water, sanitation, and hygiene (WASH), of which 53% occur in sub-Saharan Africa (1). Similarly, 4.6% of the global disability-adjusted life years (DALYs) can be attributed to inadequate WASH (1). These numbers are likely to be underestimating the true effects of WASH on the global burden of diseases, as they only stem from quantifiable effects. Examples are malaria, diarrheal diseases, soil-transmitted helminthiasis, and Schistosomiasis, which are often neglected or not representatively reported (1). Moreover, important health outcomes such as mental health or maternal and neonatal adverse health effects are not included in the calculations for the health effects attributable to insufficient WASH.

Despite recent efforts to increase hygiene during the coronavirus disease 2019 (COVID-19) pandemic, one third of the global population lacked access to basic hygiene in 2020 (2). Basic hygiene is defined as having a handwashing facility on premises with water and soap (3). On the African continent, more than half of the population did not have access to basic hygiene and 28% did not have any handwashing facility (3). When considering the regions of Africa, West African countries have the worst access to basic hygiene services, with 35% of the population not having any handwashing facility. Within the countries, inequalities persist between geographic regions and urban and rural areas (3).

Hand hygiene is crucial to sustain individual and community health. Without proper hand hygiene, pathogens can be easily transmitted from faecally contaminated hands (e.g. after using the toilet, changing diapers, handling animal products) to other people's hands, eyes, and mouths (4). Hence, inadequate hand hygiene can increase the risk for transmission of diarrheal, respiratory, and skin diseases (5-7). Scientific literature reviews report that handwashing education can reduce diarrheal disease prevalence by 23-40% (4-6), respiratory disease prevalence by 16-21% (4, 7), and school absenteeism due to gastrointestinal diseases by 29-57% (8).

